12.3.2.4. Analysis of Secondary Efficacy Endpoints

Percentage of Urine Samples Negative for Illicit Opioids

This variable will be defined in the manner per EMA's request. This variable will serve as the primary efficacy variable for EMA NDA and will not be applicable for US NDA submission.

Percent negative urine samples will be derived after applying missing value imputation. This variable will be analyzed via an analysis of variance (ANOVA) model with treatment effects. The difference between the two treatments in percent negative urine samples will be obtained from this model and the two-sided 95% confidence interval for the treatment difference will be presented.

An analysis of non-inferiority in the primary efficacy variable between the two treatments arms will be performed using a margin of 11% point.

Non-inferiority will be concluded if the two-sided 95% confidence interval for the difference between the percent negative urine samples (Active- Control) is above -0.11 .

Cumulative Distribution Function (CDF) of Percent Samples that are Negative for Illicit Opioid (Week 5-24)

Percent negative samples from 14 samples (8 weekly assessments obtained from Weeks 6 to 13, plus 3 monthly assessments obtained at Weeks 17, 21, and 25 and plus 3 random samples) will be calculated for each subject. Missing samples will be imputed as positive before the percentage is derived.

The null hypothesis of no difference in the CDF of the percent of urine samples that are negative for illicit opioids over Weeks 5-24 will be tested at the 5% significance level using Wilcoxon Rank-Sum test. The empirical CDF plot will be presented.

Time to Sustained Abstinence of Opioid Use

For the purpose of deriving time to sustained abstinence of opioid use (i.e., no opioid use through the rest of treatment period for at least 2 months), the time will be define as:

- If the sustained abstinence is obtained during the scheduled visit, time is the number of days between randomization day to the scheduled visit day. For example, if first sustained abstinence is obtained at the Week 8 visit, the time would be 56.
- If the first sustained abstinence is obtained during a random test, time is the number of days between randomization day to the day that random sample is obtained (Random Sample Date – Randomization Date).

Definition for evidence of illicit opioid use and rules for missing value imputation will be outlined in the SAP.

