9.1.1 DERIVATION OF RESPONSE RATE

For the purpose of deriving the RR, the following rules will be used:

Time Windows for Illicit Opioid Use Assessment

For easy discussion, unless otherwise stated a window denoted as Week (x+, y) for efficacy assessment is a window that covers a period between Week x +1 day to Week y day (exclusive of Week x day but inclusive of Week y day). A window denoted as Weeks x-y for efficacy assessment is a window that covers a period between Week x day to Week y day (inclusive of Week x day and Week y day).

Subjects will receive 12 weekly injections from Week 1 (Day 1 Week 1) through Week 12. Subjects will then receive three monthly injections at Week 13, Week 17, and Week 21. Since the last weekly dosing will occur at Week 12, the efficacy assessments collected at Week 13 reflected effects of weekly dosing in Phase 1. The Phase 1 window is Week (1+, 13). Since the last monthly dosing will occur at Week 21 Phase 2 efficacy window will be Week (13+, 25).

Due to visit date deviation, the actual days in Phase 1 and Phase 2 may not be exactly equal to 91 days (13 weeks) and 84 days (12 weeks), respectively. Similarly, for analysis purpose, weekly and monthly windows will be based on the visit windows, instead of exact 7-day and exact 30-day windows.

Evidence of Illicit Opioid Use within a Window

Subject response for Phase 1 will be based on the 12 scheduled weekly post-baseline urine samples collected from Weeks 2-13. Subject response for Phase 2 will be based on the 3 scheduled monthly urine samples collected at Weeks 17, 21, and Week 25 and the 3 random samples. Evidence of illicit opioid use within a window is defined as a positive opioid urine toxicology result or self-reported illicit opioid use within that window, including the results from random urine toxicology samples (in Phase 2) obtained within that window. Therefore, there is evidence of illicit opioid use, if self-reported illicit opioid use is present, regardless of the opioid urine toxicology result is positive or negative.

If urine toxicology samples are missing, for example, due to missing scheduled visit, early discontinuation of the study, or subject's refusal to provide the samples (scheduled or random samples), the results will be imputed as positive according to the Missing Value Imputation rules discussed in Section 9.1.3 of the SAP.

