9.2.2 TIME TO SUSTAINED ABSTINENCE OF OPIOID USE

For the purpose of deriving time to sustained abstinence of opioid use (i.e., no opioid use through the rest of treatment period for at least two months), the time will be defined as:

- If the sustained abstinence is obtained during the scheduled visit, time is the number of days between randomization day to the scheduled visit day. For example, if first sustained abstinence is obtained at the Week 8 visit, the time would be 56.
- If the first sustained abstinence is obtained during a random test, time is the number of days between randomization day to the day that random sample is obtained (Random Sample Date – Randomization Date).

The same definition for evidence of illicit opioid use (see Section 9.1.1) and the same rules for missing value imputation (see Section 9.1.3) will be used in the calculation.

Time to sustained abstinence of opioid use will be analyzed via a log-rank model with treatment effects. Time to event “Survival” curve will be presented using Kaplan-Meier method. Median time to event and the 95% confidence interval of the median times will be presented, if estimable. In this time to event analyses, subjects who do not have any opioid-positive results during the entire study and who do not have any opioid-positive results before discontinuing from the study will be censored at Day 175 (Week 25 day), the day when the last sample will be obtained.

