9.3.5 PERCENT OF SUBJECTS WITH NO ILLICIT OPIOID USE BY TIME POINT

For the purpose of deriving percent of subjects with no illicit opioid use by month, the same definitions for monthly window and evidence of illicit opioid use (see Section 9.1.1) and the same rules for missing value imputation (see Section 9.1.3) will be used in the calculation.

The treatment differences in these by month variables will be analyzed using chi square tests. The percentages for each treatment and between treatment percentage differences will be estimated. The 95% confidence intervals of the estimates will be presented using normal approximation.

The overall treatment difference will be tested via Wei and Lachin procedure. In this analysis, missing values were not imputed.

9.3.6 CUMULATIVE PERCENTAGE OF SUBJECTS WITH EVIDENCE OF NO ILLICIT OPIOID USE BY TIME POINT AFTER 2 MONTHS OF TREATMENT

The cumulative percentage of evidence of no illicit opioid use will be calculated for all post baseline scheduled visits after two months of treatment (from Week 9 to Week 25). The same definition for evidence of illicit opioid use (see Section 9.1.1) and the same rules for missing value imputation (see Section 9.1.3) will be used in the calculation. As the percentage is derived on a cumulative basis, subject will be included in the numerator (i.e., users) at a given scheduled visit, if the subjects have evidence of use at any prior visits or at the current visit.

The cumulative percentages by month will be analyzed using chi square tests. The percentages for each treatment and between treatment percentage differences will be estimated. The 95% confidence intervals of the estimated treatment differences will be presented.

The overall treatment difference will be also tested via Wei and Lachin procedure. In this analysis, missing values were not imputed.

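### Time to sustained abstinence censors subjects with no opioid-positive result, against its own event definition; on the post-baseline reading this mainly costs power for hypothesis 3

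*SAP*

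**What the plan says.** SAP 9.2.2 describes sustained abstinence as "no opioid use through the rest of treatment period for at least two months". Protocol 12.3.2.4 has the same definition: "no opioid use through the rest of treatment period for at least 2 months". Time runs from randomization to the visit or random sample at which sustained abstinence is first obtained; the worked example is that "if first sustained abstinence is obtained at the Week 8 visit, the time would be 56".

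The only censoring rule, the same in both documents, is that "subjects who do not have any opioid-positive results during the entire study and who do not have any opioid-positive results before discontinuing" the study "will be censored at Day 175 (Week 25 day), the day when the last sample will be obtained".

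SAP 9.2.2 takes its definition of illicit use from 9.1.1 and its missing-data rule from 9.1.3, under which every missing urine sample is imputed as positive. The analysis is a log-rank test with Kaplan-Meier curves. In SAP 9.5 superiority on this endpoint is hypothesis 3 of five ordered hypotheses. It is tested only if superiority has been shown on the distribution of percent negative samples (hypothesis 1) and on response rate (hypothesis 2). Both retention tests (hypotheses 4 and 5) come after it. SAP 9.5 places the abstinence comparison after 8 weeks of treatment; SAP 9.2.2 sets no such start.

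**The concern.** Censoring subjects without a positive result suits a time-to-first-use endpoint, where they are the ones who never have the event. Here the event is abstinence, and the subject with every post-baseline assessment present and negative reaches it sooner than anyone. The rule turns the best outcome into a non-event followed to the last day, indistinguishable from continued use.

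The group that does need a censoring rule, subjects with positive results who never reach sustained abstinence, has none in either document.

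If CAM2038 produces more never-positive completers than sublingual buprenorphine, the log-rank test discards that advantage. Hypothesis 3 can then fail for a coding reason, and the retention hypotheses cannot be tested.

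**Working it through.** **1. Who is affected.**

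| Subject | By the event definition | By the censoring sentence (post-baseline reading) |
|---|---|---|
| All post-baseline assessments present and negative | Event at first eligible visit | Censored at Day 175 |
| Positive early, then negative to the end for at least two months | Event at onset of abstinence | Event at onset of abstinence |
| Never positive, then drops out | No event, because later samples are imputed positive (SAP 9.1.3) | Censored at Day 175 |
| Positive results, abstinence never sustained | No event | No rule given |

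Only the first row is contradictory. Never-positive dropouts are not miscoded.

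**2. Which samples count.** SAP 9.1.1 supports the post-baseline reading: "Subject response for Phase 1 will be based on the 12 scheduled weekly post-baseline urine samples collected from Weeks 2-13", with a Phase 1 window that begins after Week 1. SAP 9.3.6, covering "all post baseline scheduled visits after two months of treatment (from Week 9 to Week 25"), counts as users only those with evidence of use: "subject will be included in the numerator (i.e., users) at a given scheduled visit, if the subjects have evidence of use". A never-positive completer is therefore a non-user there. Against this, Protocol 7.1 lists Screening and Day 1 among the 20 samples collected during the study.

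**3. The plan's own figure.** No power is stated for this endpoint. The stated 82% is for non-inferiority on response rate (190 per arm, 70% in both arms, margin 13.5 points). It reproduces: Φ(0.135/√(2×0.7×0.3/190) − 1.96) = Φ(0.91) = 0.819. It has no bearing on hypothesis 3.

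**4. Expected events.** The shares are assumptions: never-positive plus later abstinence, control 10%+20%, CAM2038 20%+20%, 190 per arm.
- Coherent coding: 190×0.30 = 57 against 190×0.40 = 76.
- As written: 190×0.20 = 38 against 38. The whole difference disappears.

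A rough check on the two event proportions: 0.10/√((0.3×0.7 + 0.4×0.6)/190) = 0.10/0.0487 = 2.05, and Φ(2.05 − 1.96) is about 0.54. As written the difference is 0, which leaves 2.5% in each tail.

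**5. Log-rank simulation.** Never-positive completers are events at elapsed day 7 (coherent) or censored (as written). Later onset is spread evenly over Weeks 3-13 and 17. Non-events are censored at Day 175. The entries give the chance that the test significantly favours CAM2038.

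| Control | CAM2038 | Coherent | As written |
|---|---|---|---|
| 10%+20% | 20%+20% | 58% | about 3% |
| 2%+18% | 2%+28% | 61% | 64% |
| Identical arms | Identical arms | about 2.5% | about 2.5% |

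**6. With hypotheses 1 and 2 applied.** For the first row, letting the remaining subjects give 20% or 50% negative samples, the trial passes hypotheses 1 and 2 and then wins hypothesis 3 in 35-44% (coherent) against 2-4% (as written).

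**7. Effect of missed samples.** This model generates the 18 post-baseline samples directly, with subject-level variation, 30% dropout and missing counted as positive. The figures are the chance of winning hypothesis 3 once it is reached.

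| Response, control vs CAM2038 | Missed samples | Coherent | As written |
|---|---|---|---|
| 33% vs 48% | none | 97% | 6% |
| 33% vs 48% | 5% | 87% | 34% |
| 33% vs 48% | 10% | 81% | 48% |
| 15% vs 27% | 10% | 83% | 69% |

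The loss shrinks as missed samples leave fewer subjects with a complete negative record.

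**8. Reach.** With 70% response in both arms, hypothesis 3 is reached in about 1% of trials. With assumed response advantages of 12 to 15 points it is reached in 82-87%.

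**The case against.** The strongest reply is that the premise is unsettled. If Screening and Day 1 samples count and nearly all subjects are positive then, almost nobody is censored by this sentence. That stands as a condition on the point. It also shows that two programmers could code opposite results from the same text.

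The affected group may also be small. A subject must be negative on all 18 assessments with none missed; with independent missingness of 5% or 10% per sample, only 0.95^18 = 40% or 0.90^18 = 15% have a complete record. At 2% never-positive per arm the effect is slight. This stands too, and the size must be left open.

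A reader might infer that the rule could also create or inflate a claim for CAM2038, or raise the type I error. Taken alone, the log-rank test can be pushed that way: with control 25%+10% and CAM2038 10%+20%, it favours CAM2038 in 79% as written against 0.1% coherently. But the SAP does not run that test alone. Control has the higher total abstinence there, and hypotheses 1 and 2 were both passed in 0 of 1,000 simulated trials at each setting. Three further results point the same way:
- With equal abstinence from Week 9 in both arms and never-positive shares of 20% (control) and 10% (CAM2038), a false claim after hypotheses 1 and 2 occurs in 0.4-1.0%.
- With control 15%+15% and CAM2038 15%+25%, the full sequence is won in 22-23% as written against 24-25% coherently, so nothing is gained.
- With identical arms the error rate is kept.

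A created difference survived the sequence only after adding a further assumption, that 40% of CAM2038 subjects against 5% of controls are occasional users who still count as responders. That is too special to rest the point on.

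**Conclusion.** The censoring sentence contradicts the event definition if it refers to post-baseline samples, which is the reading that SAP 9.1.1 suggests but 9.2.2 does not fix. The consequence is mainly loss of power for hypothesis 3, and so for both retention tests, when CAM2038 has more never-positive completers. Under the assumed shares of 10% and 20% the loss is from 58% to about 3% for the test alone, and from 35-44% to 2-4% once hypotheses 1 and 2 are required.

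These sizes rest on shares that the documents do not give, and range from near-total loss to almost no effect. A reversed sign, which a reader might take as a separate harm, has the same consequence in this sequence as a hidden benefit: superiority is not shown. A false or inflated claim for CAM2038 is largely blocked by hypotheses 1 and 2 and is not part of this point. The primary endpoint and safety are unaffected. It should be fixed, because the contradiction is plain and the repair is cheap.

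**What to change.** Before unblinding, in SAP 9.2.2 and Protocol 12.3.2.4:

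1. Delete the censoring sentence. Count subjects with all post-baseline assessments (Week 2 to Week 25) present and negative as events at the first assessment at which onset may count.
2. State that starting assessment once, for SAP 9.2.2 and 9.5 together: Week 9 if abstinence after 8 weeks of treatment is meant, in line with SAP 9.3.6. Otherwise remove the 8-week wording from 9.5.
3. Censor at the end of the treatment period only subjects who do not reach sustained abstinence, with dropouts handled by the missing-equals-positive rule in SAP 9.1.3.

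Two minor clarifications belong in the same edit. Name the last nominal visit at which onset may count; with two months taken as 8 weeks this is Week 17, since (25 − 17)×7 = 56 days. Use assessment date minus randomization date for scheduled and random samples alike. Protocol 7.1.2 makes Day 8 the start of Week 2, so nominal Week 8 is 7×(8 − 1) = 49 elapsed days and Week 25 is 7×(25 − 1) = 168, where 9.2.2 has 56 and 175.

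The cost is wording and derivation code. No new data are needed.

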9.2.3 PERCENT OF SUBJECTS REMAINING IN THE STUDY (RETENTION RATE)

The percentages for each treatment and between treatment percentage differences will be estimated. The 95% confidence intervals of the estimated treatment differences, based on a normal approximation, will be presented. In addition, the retention rate will be analyzed using a chi square test.

An analysis of non-inferiority in this variable between the two treatments arms will be performed using a margin of 15% point. Non-inferiority will be concluded if the two-sided 95% confidence interval for the difference in retention rate (Active- Control) is above 15%.

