12.3.2. Analysis of Efficacy Measures

12.3.2.1. Analysis of the Primary Efficacy Endpoint

The responder definition will be derived based on urine samples obtained from Weeks 10, 11, 12 and 13 in Phase 1 and samples obtained at Weeks 17 (Month 1), 21 (Month 2) and 25 (Month 3) and at the 3 random samples in Phase 2.

To be a responder for Phase 1, the subject must have no evidence of illicit opioids use at Week 13 and have no evidence of illicit opioids use for at least 2 out of the three weeks from Week 10 to Week 12. To be a responder for Phase 2, the subject must have no evidence of illicit opioids use at Month 6 (last illicit opioids use assessment in Month 6 or Week 25) and have no evidence of illicit opioids use in 5 out of the 6 illicit opioids use assessments in Phase 2. To be a responder for the study, the subject must be a responder for both Phases 1 and 2. Evidence of illicit opioid use is defined as a positive opioid urine toxicology result or a self-reported illicit opioid use.

The primary efficacy variable will be RR. The proportion of responders will be calculated in both treatment arms.

An analysis of non-inferiority in the primary efficacy variable between the two treatments arms will be performed using a margin of 13.5% point.

Non-inferiority will be concluded if the two-sided 95% confidence interval for the difference between the probabilities of response (Active- Control) is above -0.135 . The 95% confidence interval, (LB, UB), will be derived using normal approximation:

$$LB = (P_T - P_C) - 1.96 * (1/N_T * P_T * (1 - P_T) + 1/N_C * P_C * (1 - P_C))^{0.5}, \text{ and}$$
$$UB = (P_T - P_C) + 1.96 * (1/N_T * P_T * (1 - P_T) + 1/N_C * P_C * (1 - P_C))^{0.5}, \text{ where}$$

P_T and P_C are observed proportions of the responders for the treatment and the control, respectively, and N_T and N_C are the sample sizes for the treatment and the control, respectively.

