9.1.2 PRIMARY ANALYSIS

The primary analysis of RR will be performed based on the ITT population.

An analysis of non-inferiority in the primary efficacy variable between the two treatments arms will be performed using a margin of 10% point.

Non-inferiority will be concluded if the two-sided 95% confidence interval for the difference between the probabilities of response (Active- Control) is above -0.10 . The 95% confidence interval, (LB, UB), will be derived using normal approximation:

$$\text{LB} = (P_T - P_C) - 1.96 * (1/N_T * P_T * (1 - P_T) + 1/N_C * P_C * (1 - P_C))^{0.5}, \text{ and}$$
$$\text{UB} = (P_T - P_C) + 1.96 * (1/N_T * P_T * (1 - P_T) + 1/N_C * P_C * (1 - P_C))^{0.5}, \text{ where}$$

P_T and P_C are observed proportions of the responders for the treatment and the control, respectively, and N_T and N_C are the sample sizes for the treatment and the control, respectively.

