9.5 ADJUSTMENTS FOR MULTIPLICITY

There are a number of hypothesis testings that will be performed for this study. To control overall Type I error rate at 5%, a closed testing procedure will be employed (Dmitrienko 2004, Dmitrienko, Offen, Westfall 2003). Specifically, the following ordered hypotheses will be tested:

1. Superiority for CDF of percent samples that are negative for illicit opioids (Weeks 5-25);
2. Superiority for the primary efficacy variable, RR (Weeks 2-25);
3. Superiority of active treatment over the control for time to sustained abstinence after 8 weeks of treatment;
4. Non-inferiority with margin of 15% for retention rate;
5. Superiority of active treatment over the control for retention rate.

In this procedure, a comparison will be eligible for non-inferiority or superiority testing only if all previous comparisons, if any, were successfully established at the two-sided 5% significance level.

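### The retention non-inferiority rule in SAP 9.2.3 has the wrong sign: it requires the interval to lie above +15 points instead of -15, and so also blocks the superiority test that follows

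*SAP*

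**What the plan says.** SAP 9.2.3 introduces a formal test: "An analysis of non-inferiority in this variable between the two treatments arms will be performed using a margin of 15% point". The next sentence gives the decision rule: "Non-inferiority will be concluded if the two-sided 95% confidence interval for the difference in retention rate (Active- Control) is above 15"%.

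SAP 9.5 places retention twice in a fixed testing order. Step 4 is "Non-inferiority with margin of 15% for retention rate" and step 5 is "Superiority of active treatment over the control for retention rate". Each step may be tested only if every earlier one has succeeded.

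The other non-inferiority rules use the same direction of difference with a negative limit. In SAP 9.1.2 (10-point margin) the interval must show that the "difference between the probabilities of response (Active- Control) is above -0.10". In Protocol 12.3.2.1 (13.5-point margin) it must show that the "difference between the probabilities of response (Active- Control) is above -0.135". Protocol 12.3.2.4 uses -0.11 for percent negative urines, with an 11-point margin.

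For retention, Protocol 12.3.2.4 gives only a chi-square test and a confidence interval. Protocol 12.3.2.6 leaves the control of the significance level to the SAP. SAP 9.2.3 is therefore the only place that states a decision limit for this test.

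**The concern.** With the difference defined as active minus control, a non-inferiority margin of 15 points means ruling out that CAM2038 retention is worse by 15 points or more. The limit is -15. The printed limit is +15, which is a test of superiority by more than 15 points.

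Two consequences follow if the sentence is applied as printed. CAM2038 would fail non-inferiority on retention even when retention is equal or clearly better. Step 4 would also be harder to pass than step 5, so superiority on retention could be tested only after a much stronger result had already been shown.

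Timing matters too. SAP 3.0 requires the plan to be final before lock and unblinding. A sign corrected before then is clerical. Corrected afterwards, it changes a success criterion in a confirmatory sequence with the data in view.

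**Working it through.** **Inputs**

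- Margin of 15 points, active minus control: SAP 9.2.3.
- Interval method, SAP 9.2.3: "The 95% confidence intervals of the estimated treatment differences, based on a normal approximation, will be presented". I used the unpooled form that SAP 9.1.2 writes out for the primary endpoint.
- 190 subjects per arm: SAP 9.6. Two-sided 5% level: SAP 6.0.
- Retention rates: neither document gives any. I assumed 50, 60, 70 and 80% in the control arm.

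**Formula**

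SE = sqrt(pC(1-pC)/190 + pT(1-pT)/190), and the lower limit is LB = observed difference - 1.96 × SE. With true difference d, the probability that LB exceeds a limit L is Φ((d - L)/SE - 1.96).

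**Step 1: reproduce the plan's own power figure**

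SAP 9.6 states about 82% power for the primary endpoint with 70% response in both arms and a 13.5-point margin. SE = sqrt(2 × 0.21/190) = 0.0470, and Φ(0.135/0.0470 - 1.96) = 81.9%. The formula reproduces the plan's figure. The SAP gives no power figure for retention.

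**Step 2: equal true retention (d = 0)**

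Worked case at 60%: SE = sqrt(2 × 0.24/190) = 0.0503.

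- Limit -15: Φ(0.15/0.0503 - 1.96) = 84.7%.
- Limit +15: Φ(-0.15/0.0503 - 1.96) = 3.8e-7.

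| Retention, both arms | SE | P(LB > +15), as written | P(LB > -15) |
|---|---|---|---|
| 50% | 0.0513 | 5.2e-7 | 83.2% |
| 60% | 0.0503 | 3.8e-7 | 84.7% |
| 70% | 0.0470 | 1.3e-7 | 89.1% |
| 80% | 0.0410 | 9.8e-9 | 95.5% |

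Exact binomial enumeration of the same interval agrees: 6.6e-7 down to 1.1e-8 for the written rule, and 83.5 to 95.5% for the -15 rule.

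**Step 3: CAM2038 truly better**

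- 60% against 75%: SE = sqrt((0.24 + 0.1875)/190) = 0.0474. Written rule: Φ(0 - 1.96) = 2.5%. Plain superiority: Φ(0.15/0.0474 - 1.96) = 88.5%. Limit -15: above 99.9%.
- True advantage of 10 points, control 50 to 80%: written rule 0.04 to 0.16%; plain superiority 50 to 79%.
- True advantage of 20 points, control 50 to 70%: written rule 17 to 24%. At 25 points: 55 to 78%.

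**Step 4: what would have to be observed**

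Smallest CAM2038 count out of 190 that meets each limit, with the observed difference in points:

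| Control retained | LB > +15 (as written) | LB > 0 (superiority) | LB > -15 |
|---|---|---|---|
| 95 (50%) | 142 (+24.7) | 114 (+10.0) | 86 (-4.7) |
| 114 (60%) | 160 (+24.2) | 133 (+10.0) | 105 (-4.7) |
| 133 (70%) | 176 (+22.6) | 150 (+8.9) | 123 (-5.3) |
| 152 (80%) | not attainable | 167 (+7.9) | 140 (-6.3) |

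In the last row, even 190/190 retained on CAM2038 gives LB = 0.20 - 1.96 × sqrt(0.16/190) = 0.143, which is below 0.15.

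**Step 5: effect on the hierarchy**

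Plain superiority at step 5 needs an observed advantage of about 8 to 10 points. The printed step 4 needs about 23 to 25 points where it can be met at all. Any result that passes the printed step 4 has already passed step 5, so the order makes sense only with the limit at -15.

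**The case against.** The best reply is that this is an evident slip with little practical reach. The preceding sentence calls 15 points a non-inferiority margin, step 4 of SAP 9.5 says the same without a sign, and the three parallel rules carry a minus sign, so only one reading is sensible. The wording in SAP 9.5 contains no error of its own.

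The test is also rarely reached. Three superiority tests must succeed first. Under the plan's own assumption of 70% response in both arms, superiority on the primary variable in favour of CAM2038 succeeds about 2.5% of the time, so step 4 would open in at most about 2.5% of trials. The primary non-inferiority conclusion does not depend on it. Finally, a minus sign lost in conversion of the file cannot be wholly excluded, although minus signs survive in the parallel rules.

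Most of this stands, but it limits reach and does not rescue the rule. The probabilities above are conditional on reaching step 4, and the error matters most where CAM2038 really is superior on the earlier endpoints. It is also true that the printed rule can be passed if the retention advantage is 20 points or more. None of these points supplies a correct limit, and a pre-specified threshold should not rest on the reader inferring a missing sign.

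**Conclusion.** The concern holds. The decision limit printed in SAP 9.2.3 contradicts the margin stated in the sentence before it and the convention used elsewhere in both documents. At 190 per arm and equal retention of 50 to 80%, the printed rule is met with probability at most 5.2e-7, where a -15 limit would be met 83 to 95% of the time. Even a true 15-point advantage meets it only 2.5% of the time. Step 5 would be blocked in nearly all trials with a true advantage of up to about 15 points that reached step 4.

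These sizes rest on assumed retention rates, the unpooled normal interval, and all 190 subjects per arm entering the analysis. That the limit is wrong does not depend on any of these. Primary non-inferiority is not affected.

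**What to change.** In SAP 9.2.3, replace the decision sentence with: retention on CAM2038 is declared non-inferior when the lower limit of the two-sided 95% interval for CAM2038 minus SL BPN exceeds -15 percentage points. Repeat the signed limit at step 4 of SAP 9.5, so that both sections give the same rule.

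The cost is a short text correction in a SAP revision. The margin, sample size, testing order and design are unchanged. It should be approved before database lock and unblinding.
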